10.8.11 Investigator Assessment of Respiratory Status

For subjects in Cohorts 4 & 5, a listing will be created of the investigator's assessment of the subject's respiratory status relative to baseline (better, worse, or the same) at Day 57-FU.

10.8.12 Other Assessments

All other safety assessments not detailed in this section will be listed but not summarized or statistically analyzed.

10.9 Data Safety Monitoring Board

An independent DSMB experienced in the oversight and monitoring of the conduct of clinical trials will determine whether dose escalation should proceed. The DSMB will be comprised of a biostatistician and two pulmonologists with expertise in interstitial lung diseases. The DSMB members' responsibilities and the process for data reviews and dose-escalation are described in the DSMB Charter.

Dose escalation will be based on the DSMB's review of unblinded PK and safety data through Day 15 from the initial 4 (of 8) subjects administered BG00011 or placebo (3:1, respectively) in each cohort. Safety assessments will include a review of AEs, vital signs, physical examination, clinical laboratory tests, and pulse oximetry from these visits. In order to allow for compilation and evaluation of the data, it is anticipated that the DSMB will convene approximately 9-10 weeks after the first 4 subjects in the previous cohort are initially dosed.

Serious adverse events will be provided to the DSMB on an ongoing basis throughout the study. Updated safety (including BAL, PFTs, and HRCT results) and PK information on all participants will be provided in each subsequent DSMB data package. For example, at the DSMB meetings for Cohorts 2 and 3, updated safety and PK data will be available through at least week 8 of the follow-up period (i.e., complete PK data through the dosing phase and follow-up BAL, PFT, and HRCT) for all participants in Cohorts 1 and 2, respectively.

10.10 Pharmacodynamic Analyses

Secondary objectives of this study are to assess the effect of BG00011 on biomarkers isolated from BAL and peripheral blood in subjects with IPF. Listings and summary tables of expression level of 7 prespecified genes (Table 2) will be provided by treatment group and visit. A listing and summary table of ratio of pSMAD2 to tSMAD2 levels will be provided by treatment group and visit. Additional analyses of gene expression data from serum or BAL may be provided in a separate report.

Table 2: Pre-Specified Genes

Gene	Gene Description
ALOX5 (Arachidonate 5-lipoxygenase)	A member of the lipoxygenase family of enzymes that transforms arachidonic acid into pro-inflammatory leukotrienes. Associated with fibrotic lesions in IPF lung tissue.
ETS1 (v-ets erythroblastosis virus E26 oncogene homolog 1)	A transcription factor that negatively regulates TGF- β induced collagen expression and inhibits IL-1b induced lung inflammation and MUC5AC

	production.
FN1 (fibronectin)	An extracellular matrix protein that plays a major role in cell adhesion, growth, migration, and differentiation. Altered fibronectin expression is associated with fibrosis.
OLR1 (oxidized low density lipoprotein [LDL] receptor 1)	A LDL receptor belonging to the C-type lectin superfamily. Internalizes and degrades oxidized LDL. Upregulates angiotensin II activity and knockout protected against renal injury and fibrosis. Knockout also decreases TGF- β induced collagen production from cardiac fibroblasts.
PAI-1 (plasminogen activator inhibitor-1; also known as SERPINE1)	A serine protease inhibitor and the principal inhibitor of tissue plasminogen activator and urokinase, the activators of plasminogen and hence fibrinolysis. PAI-1 inhibits the activity of matrix metalloproteinases and plays a significant role in the progression to fibrosis.
TGM2 (transglutaminase 2)	Catalyzes the crosslinking of extracellular matrix proteins including fibronectin and collagen. Acts as a co-receptor with beta integrins for binding to fibronectin enhancing cell adhesion and migration. Can enhance expression and maturation of fibrillar fibronectin.
TREM1 (triggering receptor expressed on myeloid cells 1)	Amplifies monocyte/macrophage- and neutrophil-mediated toll-like receptor inflammatory responses by stimulating release of pro-inflammatory chemokines and cytokines. Elevated soluble serum TREM1 levels are negatively correlated with pulmonary function in scleroderma subjects.

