9. DEFINITION OF ANALYSIS POPULATIONS

The “Safety” population will consist of all subjects who received at least one dose of BG00011 or placebo.

The “Pharmacodynamic” population will consist of all subjects who received at least 1 multiple dose injection of BG00011 and have a corresponding sample collected for BAL and/or blood biomarkers (e.g., Visit 16 Day 8-FU).

All protocol deviations that occur during the study will be considered for their severity/impact prior to treatment assignment unblinding and will be taken into consideration when subjects are assigned to analysis populations. Details of subject assignment to the analysis populations will be listed.

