10. STATISTICAL METHODOLOGY

10.1 General

Data listings will be provided by treatment group, subject and visit, if applicable. Summary statistics and statistical analyses will only be presented for data where detailed in this SAP. For continuous data, summary statistics will include the arithmetic mean, arithmetic standard deviation (SD), median, minimum (Min), maximum (Max) and n; for log-normal data the geometric mean and geometric coefficient of variation (CV) will also be presented. For categorical data, frequency count and percentages will be presented. Data listings will be provided for all subjects up to the point of withdrawal, with any subjects excluded from the relevant population highlighted. Summary statistics and statistical analyses will generally only be performed for subjects included in the relevant analysis population. For the calculation of summary statistics and statistical analysis, unrounded data will be used.

Due to the small number of subjects expected to enroll at each participating center, all summaries and analyses will be performed using data pooled across centers. Data for BG00011 treated subjects will be grouped by treatment group. Data for all placebo subjects, regardless of treatment group, will be treated as one group. Data will be summarized and presented by treatment group, defined as each of the BG00011 dose groups and the combined placebo group. Data will be listed by treatment group. Exposure to study medication will be tabulated by treatment group.

Mean change from baseline is the mean of all individual subject’s change from their baseline value. Each individual change from baseline will be calculated by subtracting the individual subject’s baseline value from the value at their subsequent visit(s). The individual subject’s change from baseline values will be used to calculate the mean change from baseline using a SAS[®] procedure such as Proc Univariate.

Data analyses will be performed using SAS[®] Version 9.1.3 or greater.

As previously stated (Section 4), this document describes the planned analyses for this Phase 2a study evaluating the safety, tolerability, PK, immunogenicity, and impact on BAL and peripheral blood biomarker of multiple doses of BG00011 in subjects with IPF. Some of the analyses described in this SAP will be performed by outside vendors. These data will be imported to the Biometrics database for study 203PF201 or, alternatively, provided as separate reports.

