13. CHANGES FROM THE PREVIOUS STATISTICAL ANALYSIS PLAN

Several changes were made to SAP version 2.0 that differed from the SAP version 1.0. All changes to the SAP were finalized prior to database lock and unblinding. In addition to editorial updates, the following changes were made:

- A test for trend analysis will not be performed to assess the relationship between dose level and incidence of antibodies due to small sample sizes.
- Many of the efficacy analyses described in Section 10.8 of SAP version 1.0 will not be performed under this SAP. Additional analyses of gene expression data from serum or BAL will be provided in a separate report. ETS1 and tSMAD2 were added as biomarkers to analyze.
- The “Efficacy” analysis population was renamed to the “Pharmacodynamic” population to more accurately reflect its purpose. Also, only 1 injection of BG00011 will be necessary for part of the requirement to be included in this population, rather than the 5 injections noted in SAP version 1.0.
- The PK methods and analysis will be described in a separate PK analysis plan.

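### The Pharmacodynamic population, read literally, leaves placebo out of the biomarker tables, and those tables show levels only, with no within-subject change

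*SAP*

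**What the plan says.** SAP Section 5 lists among the secondary objectives an assessment of the effect of BG00011 on biomarkers from BAL and peripheral blood, and Section 10.10 repeats it. The planned output in Section 10.10 is:

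- for the genes: "Listings and summary tables of expression level of 7 prespecified genes (Table 2) will be provided by treatment group and visit";
- for the SMAD2 ratio: "A listing and summary table of ratio of pSMAD2 to tSMAD2 levels will be provided by treatment group and visit".

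Section 9 defines the Pharmacodynamic population as "all subjects who received at least 1 multiple dose injection of BG00011 and have a corresponding sample collected for BAL and/or blood biomarkers". The Safety population, defined just above it, names both BG00011 and placebo.

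Section 10.1 pools all placebo subjects into one group and counts that group among the treatment groups. Section 10.2 gives the same definition. Section 10.1 also says: "Summary statistics and statistical analyses will generally only be performed for subjects included in the relevant analysis population".

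A change measure is named for lung function (Section 10.8.6, percent change), BAL MMP-12 (Section 10.8.7, percent change from screening) and pulse oximetry (Section 10.8.9, change from baseline). None is named in Section 10.10.

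**The concern.** The objective concerns an effect. In a placebo-controlled study with samples before and after dosing, an effect is read from how each subject changed and from how that compares with placebo. The plan is weak on both.

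- **Control.** Section 9 and the treatment-group definition cannot both govern the same table. If Section 9 wins, the biomarker summaries have five active columns and no control column.
- **Change.** Visit-by-visit level summaries let a reader form the ratio of two visit summaries, but they do not show how much individual changes vary. Section 9 requires no baseline sample and accepts BAL and/or blood, so the tables also do not say how many subjects contribute a pair.

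At stake is how readable one secondary objective is. No decision rule, error rate or sample size depends on it.

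**Working it through.** **Plan's own figures.** The SAP gives no SD, correlation or precision target for the biomarkers. Its one probability, 82% in Section 8, reproduces (1 − 0.75^6 = 0.822), but it concerns observing an event among 6 subjects and does not bear on this point.

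**Step 1: who is in the tables.**

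| Place | Placebo included? |
|---|---|
| Section 9, Safety population | Yes, named |
| Section 9, Pharmacodynamic population | No, only BG00011 recipients |
| Sections 10.1 and 10.2, treatment group | Yes, as one combined group |
| Section 10.10, reporting by treatment group | Yes, through that definition |
| Section 10.1, summaries limited to the relevant population | No, if the Section 9 wording is applied |

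Section 6 plans 2 placebo subjects in each of 5 cohorts: 5 × 2 = 10 of 40, or 25% of the sample. Section 10.1 keeps all subjects in the listings and highlights those outside the relevant population. The loss would therefore fall on the summary tables, not on the listings.

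**Step 2: is a change planned elsewhere in the SAP?** Section 10.1 defines how a change from baseline is computed (a plain difference) but does not say which variables get one. Sections 10.8.6, 10.8.7 and 10.8.9 each name their change explicitly. Section 10.10 does not, and it does not state the scale of expression level. A plain difference suits expression data only if they are already on a log scale.

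**Step 3: what pairing adds.** Work on the log scale with n = 6 per dose group, equal SD σ at both visits and within-subject correlation ρ. Both σ and ρ are assumptions.

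- Point estimate with complete pairs: mean(log post) − mean(log pre) = mean(log post − log pre). The ratio of visit geometric means equals the geometric mean of the paired ratios, so pairing does not alter it.
- Nominal 95% half-width that a reader would form from the level tables, ignoring pairing: t(10) × σ × √(2/6) = 2.228 × 0.577σ = 1.286σ.
- Half-width from paired changes: t(5) × σ × √(2(1 − ρ)/6), with t(5) = 2.571.

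| ρ (assumed) | Paired half-width | Paired / unpaired |
|---|---|---|
| 0.3 | 2.571 × 0.483σ = 1.242σ | 0.97 |
| 0.5 | 2.571 × 0.408σ = 1.050σ | 0.82 |
| 0.7 | 2.571 × 0.316σ = 0.813σ | 0.63 |

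The ratio does not depend on σ. Break-even is at ρ = 1 − (2.228/2.571)² = 0.249. Below that, the lost degrees of freedom cancel the gain.

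**The case against.** Several points on the other side are fair.

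- **The table shells may show a change column.** Section 4 places the detailed table descriptions in a separate shell document that is not at hand. This stands as a caveat. The SAP itself does not commit to a change for these measures, although it does for three others.
- **Section 10.1 does not forbid a change.** A reader might infer a prohibition from "Summary statistics and statistical analyses will only be presented for data where detailed in this SAP". That sentence restricts which data are summarised, not each statistic, and Section 10.10 does detail these data. The change is unplanned, not barred.
- **The log-scale tools exist.** Section 10.1 already provides the geometric mean and geometric CV for log-normal data. This stands, and it makes the fix smaller.
- **A separate report may cover it.** "Additional analyses of gene expression data from serum or BAL may be provided in a separate report". That is optional, fixes no content and concerns gene expression, so it does not mention pSMAD2/tSMAD2. A reader might also infer a contradiction from the firmer wording in Section 13. That section lists changes from the previous SAP, so the difference is not an error.
- **The pairs can be read from the listings.** True: with 6 active subjects per cohort a reader can form them by hand. No group summary of them is planned.
- **The reduced scope was deliberate.** Section 13 says that many earlier efficacy analyses were dropped. That supports a descriptive plan, but it neither says that placebo should leave the tables nor explains why MMP-12 keeps a change and the seven prespecified genes do not.

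**Conclusion.** The point holds in two parts. The Section 9 wording contradicts the treatment-group reporting in Sections 10.1, 10.2 and 10.10. Taken literally, it removes all 10 planned placebo subjects from the summaries of a secondary objective. A reader might go further and conclude that the sponsor intends to exclude placebo. The documents do not support that, because the population rule in Section 10.1 applies only generally and the other sections point the other way. The wording is wrong as it stands, and the intent is unclear.

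The missing within-subject change is a nearly free improvement of low to moderate weight. A reader might infer that level tables give a biased or less efficient estimate of fold change. They do not: with complete pairs the estimate and its true sampling variance are the same. Only the spread that a reader can derive differs, and the size of that difference rests on an assumed correlation: about 3%, 18% or 37% narrower on the log scale at 0.3, 0.5 or 0.7, and no narrower below about 0.25. The SAP plans no intervals for these measures, so these figures only illustrate the value of a paired summary.

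**What to change.** 1. **Section 9.** Redefine the Pharmacodynamic population as subjects who received at least one injection of BG00011 or placebo and have a corresponding BAL or blood biomarker sample.
2. **Section 10.10.** State the scale on which expression level is reported. For subjects with both a baseline and a post-dose sample, add the number of pairs and the within-subject change for each of the 7 genes and for pSMAD2/tSMAD2. Use the post/pre ratio, summarised by geometric mean and geometric CV under the existing Section 10.1 rule for log-normal data, or a simple difference where the data are already on a log scale. Report by treatment group, including pooled placebo, alongside the planned level tables.

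All of this stays descriptive and needs no test. It costs one sentence in Section 9, two or three in Section 10.10 and a few table rows, with no new data collection. It should be settled before database lock and unblinding, the point by which Section 4 requires the SAP to be final.

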11. INTERIM ANALYSES

No formal interim statistical analyses are planned. An administrative interim analysis of data collected on Cohorts 1-4 may be used for internal (Biogen) decision making.

12. CHANGES FROM THE PROTOCOL SPECIFIED STATISTICAL ANALYSES

There were no changes from the protocol specified statistical analyses.

13. CHANGES FROM THE PREVIOUS STATISTICAL ANALYSIS PLAN

Several changes were made to SAP version 2.0 that differed from the SAP version 1.0. All changes to the SAP were finalized prior to database lock and unblinding. In addition to editorial updates, the following changes were made:

- A test for trend analysis will not be performed to assess the relationship between dose level and incidence of antibodies due to small sample sizes.
- Many of the efficacy analyses described in Section 10.8 of SAP version 1.0 will not be performed under this SAP. Additional analyses of gene expression data from serum or BAL will be provided in a separate report. ETS1 and tSMAD2 were added as biomarkers to analyze.
- The “Efficacy” analysis population was renamed to the “Pharmacodynamic” population to more accurately reflect its purpose. Also, only 1 injection of BG00011 will be necessary for part of the requirement to be included in this population, rather than the 5 injections noted in SAP version 1.0.
- The PK methods and analysis will be described in a separate PK analysis plan.

15. DATA PRESENTATION

Values will be presented as indicated below.

For safety data analysis:

- Report mean values to the same decimal place as the individual data to which they refer.
- Report SD and standard error (SE) of the mean to one more decimal place than the mean.
- Report Med, Min, and Max values to the same number of decimal places as the individual data to which they refer.
- Report CV, defined as the ratio of the standard deviation over the mean, as a percentage to one decimal point.
- Report n to whole numbers.

For example:

Individual Values	n	Mean	SD	SE	Min	Med	Max	CV
136, 123, 135	12	131	7.2	4.2	123	135	136	5.5%
2.3, 3.1, 2.7, 3.0	12	2.8	0.36	0.18	2.3	2.9	3.1	13.0%

15.1 Missing Data

Missing data will not be displayed in listings; the data inputs for the relevant timepoint will be left blank if the data are missing.

15.2 Presentation for Dates

Dates will be presented in format (ddmonyyyy). Dates that are missing because they are not applicable will be presented as “NA,” unless otherwise specified.

15.3 Unscheduled Assessments

Unscheduled assessments in the listings will be labeled as “Unscheduled.” Values obtained during unscheduled visits will not be presented in summary tables, unless requested by the Sponsor.

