10.8.2 Clinical Laboratory Parameters

Serum chemistry and hematology data will be summarized by treatment group and visit. Descriptive statistics will be presented at each visit by treatment group for the parameters listed below. Shift tables of the baseline value compared to each post baseline value will be presented for the following selected laboratory parameters: a) alanine aminotransferase (ALT), aspartate aminotransferase (AST), blood urea nitrogen (BUN), creatinine, direct bilirubin, glucose, and cholesterol for chemistry; and b) hemoglobin, hematocrit, white blood cell (WBC) count, neutrophil count, lymphocyte count, and platelet count for hematology. Urinalysis data and pregnancy data will be listed only. In addition, all serum chemistry, hematology and urinalysis data outside the central laboratory standard reference ranges will be listed by parameter and treatment group.

Individual subject listings of clinical laboratory parameters at each visit will be provided. Values for any serum chemistry, hematology, and urinalysis values outside the central laboratory reference ranges will be flagged on the individual subject data listings.

The following laboratory safety assessments will be included in the subject listings:

- Hematology: complete blood count (CBC) with differential and platelet counts. CBC includes red blood cells (RBCs), WBCs, hemoglobin, hematocrit, mean corpuscular volume (MCV), mean corpuscular hemoglobin (MCH), and mean corpuscular hemoglobin concentration (MCHC)
- Serum chemistry: albumin, alkaline phosphatase, ALT, AST, BUN, calcium, chloride, bicarbonate (HCO_3), creatinine, direct bilirubin, gamma-glutamyl transpeptidase (GGT), glucose, lactate dehydrogenase (LDH), magnesium, phosphorus, potassium, sodium, total cholesterol, total protein, and uric acid
- Urinalysis: including determination of the presence of protein, glucose, ketones, occult blood, and WBCs by dipstick, with microscopic examination, if indicated

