10.8.6 Pulmonary Function Tests (PFT)

Under Protocol Version 1, for screening and baseline PFTs, 3 PFTs will be performed on separate days during the screening period (within 5 weeks prior to dosing). The first of these tests will be performed before and after bronchodilator administration to determine if the subject qualifies for the study, whereas the other 2 will be averaged to serve as the subject's baseline value.

Under Protocol Version 2 and later, for screening and baseline PFTs, 2 PFTs will be performed on separate days during the screening period (within 5 weeks prior to dosing). The first of these tests will be performed before and after bronchodilator administration to determine if the subject qualifies for the study, whereas the other PFT (performed without bronchodilator administration) will serve as the subject's baseline value. If the baseline PFT does not meet quality criteria, the pre-bronchodilator screening PFT (or repeat pre-bronchodilator screening PFT, if appropriate) will be substituted as the baseline value.

PFT parameters include:

FVC: forced (expiratory) vital capacity

FEV₁: forced expiratory volume over one second

TLC: total lung capacity

DLco/Hb:carbon monoxide diffusion capacity, corrected for hemoglobin

RV: residual volume

The assessment of changes in lung function during this study will be performed by comparing the subject's follow-up PFT parameters (i.e., Visit 9 Day 29-MD and Visit 16 Day 8-FU visits) to

their baseline value. Each subject's percent change from baseline will be calculated by subtracting the individual subject's baseline value from the value at the desired time point and then dividing this calculated value by the individual subject's baseline value and multiplying by 100. The individual subject's percent change from the baseline value will be used to calculate the mean percent change from baseline for the treatment group using a SAS procedure such as Proc Univariate.

The following decreases in PFT parameters have been prospectively defined as significant and may be clinically important: TLC $\geq 8\%$, FEV₁ $\geq 12\%$, FVC $\geq 12\%$, and/or DLco/Hb $\geq 15\%$ change from the baseline value. PFTs demonstrating a potentially clinically significant decline from baseline must be confirmed by repeating the abnormal parameter. A confirmed decline in a PFT parameter will be reported as an adverse event and will be used for analysis purposes.

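### The rule on unscheduled values does not separate by-visit tables from shift tables, and it leaves inclusion to an open sponsor request

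*SAP*

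**What the plan says.** Section 15.3 has two parts. Unscheduled values stay in the listings: "Unscheduled assessments in the listings will be labeled as" unscheduled. They are kept out of the tables: "Values obtained during unscheduled visits will not be presented in summary tables, unless requested by the Sponsor". The section does not name the tables it covers, and it gives neither a criterion nor a time limit for a sponsor request.

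Section 10.8.2 says of selected chemistry and hematology parameters: "Shift tables of the baseline value compared to each post baseline value will be presented". It makes no exception for unscheduled values. It also provides that "all serum chemistry, hematology and urinalysis data outside the central laboratory standard reference ranges will be listed by parameter and treatment group".

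Section 10.8.9 summarises oxygen saturation by visit, as values and as change from baseline.

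Section 10.8.6 names two post-baseline pulmonary function visits, Day 29-MD and Day 8-FU. It adds a confirmation step: "PFTs demonstrating a potentially clinically significant decline from baseline must be confirmed by repeating the abnormal parameter". It then says: "A confirmed decline in a PFT parameter will be reported as an adverse event and will be used for analysis purposes". It does not say whether the repeat counts as unscheduled, or which of the two values is analysed.

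Section 10.8.1 bases the adverse event tables on treatment-emergent events, whatever the type of visit. Section 10.8 plans no inferential analysis.

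**The concern.** By-visit tables need one value per subject per nominal visit, so leaving unscheduled values out of them is sensible. A shift table has a different purpose, which is to show how many subjects in a group moved out of range. An extra test is often done because something looked wrong. If its result cannot enter the shift table, the table can show no shift for a subject who had one.

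The sponsor option adds a second weakness. Section 4 requires the SAP to be final before database lock and unblinding, and requires substantial deviations to be identified in the study report. Because the option is part of the SAP, using it after results are known would not clearly be a deviation. A reader of the report could not tell whether inclusion had been planned or chosen.

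What is at stake is the group-level picture for safety and tolerability, the primary objective in Section 5.

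**Working it through.** **Laboratory shift tables.** Take an ALT rise found at an unscheduled visit and normal at the scheduled visits on either side. Section 10.8.2, read literally, puts it in the shift table because it is a post-baseline value. Section 15.3, read literally, keeps it out. The SAP does not say which governs. If Section 15.3 governs, the rise appears in the subject listing and the out-of-range listing, and in the adverse event tables only if the investigator reported it as an event. It does not appear in the shift counts.

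**Oximetry.** Section 10.8.9 has by-visit statistics only. A low saturation between visits has no row in the summary and no worst-value row to fall into.

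**Pulmonary function.** Only two post-baseline visits are named, so a repeat on another day would presumably be unscheduled. The confirmed decline still reaches the tables as an adverse event, and the triggering scheduled value stays in the by-visit summary. What remains open is which number, if any, the phrase about analysis purposes refers to.

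**Size for one subject.** Inputs are the group sizes in Section 6, Table 1: 6 active subjects per cohort, 30 active in total, 10 on placebo. One shift seen only at an unscheduled visit moves the group rate from 0 to:
- one dose group: 1/6 = 16.7%
- pooled placebo: 1/10 = 10.0%
- combined active group: 1/30 = 3.3%

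**Size for a cohort, illustration only.** Section 8 gives an 82% chance of observing an event among 6 subjects when the true probability is 25%. Check: 1 − (1 − 0.25)^6 = 1 − 0.178 = 0.822, so the figure reproduces.

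Let q be the share of affected subjects whose abnormality is seen only at an unscheduled visit. The SAP gives no q, so the values below are assumptions. The chance that the cohort's summary table shows at least one affected subject is 1 − (1 − 0.25(1 − q))^6:

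| q (assumed) | Chance shown in table |
|---|---|
| 0 | 82.2% |
| 0.10 | 78.3% |
| 0.25 | 71.2% |
| 0.50 | 55.1% |
| 0.75 | 32.1% |

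Section 8 concerns observing an event at all, not tabulating a laboratory shift. The table shows only how the loss would grow with q; it does not estimate it.

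**The case against.** The strongest case on the other side has five parts.

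- **Nothing is lost from the report.** Unscheduled values are listed and labelled, out-of-range laboratory values are listed again by parameter and group, and reported events are tabulated. With 6 active subjects per cohort, a careful reader can find an individual abnormality. This stands, and it limits the weight of the point. A reader might infer that Section 15.3 removes the abnormal values from view; the document does not support that. Listings do not, however, give group rates.
- **The shift tables may be meant by visit.** They follow a sentence about summaries by treatment group and visit, and on that reading an unscheduled value has no row. This is plausible, but the wording promises every post-baseline value and states no such limit. The table shells are not at hand and might settle it.
- **The pulmonary function rules do not contradict each other.** This stands. A reader might infer a clash between the confirmation rule and Section 15.3, but a confirmed decline "will be reported as an adverse event and will be used for analysis purposes", and the event report takes it into the tables. The gap is an ambiguity about which value is used.
- **Mean change is not shown to be biased.** A reader might infer an upward bias because only declines are repeated. That would follow only if repeats replaced scheduled values. No section says they do, and if repeats are unscheduled, Section 15.3 keeps them out of the means.
- **The sponsor option can only add values.** It cannot remove scheduled ones, there is no test for it to distort, and an addition treated as an additional analysis would be disclosed under Section 4. This is fair, but selective addition after results are seen is still a choice that the SAP should fix in advance.

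**Conclusion.** The point holds in a limited form. Section 15.3 applies one rule to tables with different purposes, sits uneasily with the shift-table wording in Section 10.8.2, and leaves exceptions to an undated request. As written, the laboratory shift and oximetry summaries can understate how many subjects in a group had an abnormality.

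The extent is unknown. The SAP gives neither the number of unscheduled tests nor how often they would be the only abnormal ones. That such tests are more often abnormal is a reasonable inference; the pulmonary function repeats, which are triggered by a marked decline, are the one example in the document. The firm figure is the weight of a single subject: 17% of a dose group of 6.

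Because the analyses are descriptive, the listings are complete and adverse events are captured separately, this is a worthwhile and inexpensive clarification. It does not threaten the validity of the safety analysis.

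**What to change.** Before unblinding, replace the rule in Section 15.3 with one that covers these points:

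1. By-visit descriptive summaries use scheduled values only.
2. Each laboratory shift table, and the oximetry summary, gains a worst-post-baseline row taken over scheduled and unscheduled values together.
3. The open sponsor option is deleted, since the rule now states when unscheduled values enter a table.
4. By-visit pulmonary function means use the scheduled value; a repeat serves only to confirm the decline for the adverse event report.

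Section 10.8.2 should be worded to match, so that the by-visit shifts and the worst-value row are told apart.

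The cost is a few sentences in the SAP, one extra row per affected table and minor programming. No new data are needed, because the unscheduled values are already in the listings.
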